Measures 1-4 above will be made with commercially available devices. Blood assays will be performed in our research laboratories using standard assaying methods.

We anticipated enrolling approximately 50 healthy volunteers.

Phase II (Critically Ill Subjects):

Phase II may begin prior to Phase I completion.

Phase II will consist of trialing optimal loading and frequencies developed in phase I on a targeted population of critically ill or injured subjects who are expected to experience prolonged immobilization in the intensive care unit. Patient subjects may or may not be mechanically ventilated.

These patient subjects will be subjected to a similar series of vibration tuning protocols to maximize physiologic response.

The following will be measured:

- 1) Tissue hemoglobin oxygen saturation (StO₂) using near infrared spectroscopy of the thighs, biceps, and brain. This measure will at baseline (prior to each vibration episode), continuously during vibration, and then for 30 minutes after vibration.
- 2) Muscle contraction using a noninvasive electromyography (EMG). This measure will at baseline (prior to each vibration episode), continuously during vibration, and then for 30 minutes after vibration.

Rectus femoris muscle geometry using Ultrasound as a measure of muscle mass preservation. This measure will be made prior to the first vibration episode and then at the end of the enrollment (5 days later). Blood sampling before and after vibration (10 cc samples) to examine markers that are believed to be associated with serum glucose, lipids, inflammatory cytokines (e.g., IL-6, TNF α , IL-1 β), growth hormone, cortisol and bone turnover markers (e.g., C-terminal telopeptide of type I collagen (CTX-I) *and* tartrate-resistant acid phosphatase 5b).

Measures 1-3 above will be made with commercially available devices. Blood assays will be performed in our research laboratories using standard assaying methods. We will not measure VO₂ on patient subjects due to the complexity of the measure and need for integration into the ventilator circuit.

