Patient subjects will be recruited to undergo up to three vibration sessions per day for up to 5 days. Each vibration session is expected to last 5-10 minutes. Blood will be taken prior to the very first vibration session. A second sample of blood will be taken at the end of the last vibration session of the day for each day. A pre-vibration sample will only be obtained on the first day. Thus each patient subject will have a maximum of 5 samples taken during the course of their enrollment.

We anticipated enrolling approximately 50 patient subjects.

Potential Risk and Potential Benefit to the Subjects:

This study is believed to represent minimal risk since whole body vibration platforms are ubiquitous in the their use in the fitness industry and there are several that are FDA approved. None, however are adapted for use for patients immobilized in bed and none have the ability to have their frequencies adjusted.

The potential risks identified with the above project may include the following:

- 1) Transient muscle soreness
- 2) Bruising and discomfort from venipuncture (health volunteers). Blood from patient subjects will be taken from pre-existing intravenous catheters.
- 3) Anemia (patient subjects). We will not obtain blood from patients whose last recorded hemoglobin level is less than 8 mg/dl.
- 4) Breach of confidentiality

The potential benefits identified to the subjects include:

- 1) Knowledge that they are contributing to increasing medical knowledge and to a potential technology that will help mitigate the myopathy associated with prolonged immobility.
- 2) Potential improvement in muscle strength and reduced myopathy (patient subjects).

Statistical Analysis:

Continuous data will be presented as mean (SD) or median (IQR), while categorical data will be presented as percentages. An effect-response analysis will be conducted to describe the effect of changing frequency on the different physiologic responses using a single tone excitation as well as the multi frequency excitation. Effect-response curves will be constructed with the frequencies on the x-axis and the physiologic response on the y-axis. The threshold-effect (desired frequency) will be determined for individual physiologic changes as well as at different combinations.

References/Literature Cited:

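### The Phase II blood schedule yields up to 6 samples per patient, not the stated maximum of 5

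*Combined protocol and SAP*

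**What the plan says.** The schedule is in the Phase II (Critically Ill Subjects) section of the combined protocol and SAP, in the paragraph on vibration sessions and blood draws. It is built from these statements:

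- Duration: patients receive "up to three vibration sessions per day for up to 5 days".
- Baseline draw: "Blood will be taken prior to the very first vibration session".
- Daily draw: "A second sample of blood will be taken at the end of the last vibration session of the day for each day".
- No later baselines: "A pre-vibration sample will only be obtained on the first day".
- Conclusion: "Thus each patient subject will have a maximum of 5 samples taken during the course of their enrollment".

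The list of Phase II measures gives the volume: "Blood sampling before and after vibration (10 cc samples) to examine markers". No total volume per patient is stated. The section on potential risks lists anemia for patient subjects and adds a withholding rule: "We will not obtain blood from patients whose last recorded hemoglobin level is less than 8 mg/dl". Planned enrollment is given as: "We anticipated enrolling approximately 50 patient subjects".

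**The concern.** The maximum is introduced as a consequence of the sentences before it, yet adding those sentences up gives a different number. One of the two must be wrong, and the protocol does not say which one governs.

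The figure is the only per-patient limit on research blood draws in the protocol, and it applies to critically ill patients. Someone assessing the blood taken for research from this paragraph would use 5 samples, while the draw instructions lead to 6.

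There is also a practical conflict. For a patient sampled on every one of the 5 days, staff cannot both take each scheduled draw and stay within the limit. If they stop at 5, the day-5 value is lost. If they save a draw by omitting the baseline, the patient's only pre-vibration value is lost. With no instruction, this could be settled differently from one patient to the next.

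**Working it through.** **Inputs**, all from the Phase II section:

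- vibration days, d: 1 to 5
- pre-vibration samples: 1, on day 1 only
- end-of-day samples: 1 per vibration day, so d in total
- volume per sample: 10 cc
- patients: about 50
- stated maximum: 5 samples

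**Count as written.** Samples = 1 + d. Volume = 10 cc × (1 + d).

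| Vibration days | Pre-vibration | End of day | Total samples | Volume |
|---|---|---|---|---|
| 1 | 1 | 1 | 2 | 20 cc |
| 2 | 1 | 2 | 3 | 30 cc |
| 3 | 1 | 3 | 4 | 40 cc |
| 4 | 1 | 4 | 5 | 50 cc |
| 5 | 1 | 5 | 6 | 60 cc |

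Day 1 contributes 2 samples and days 2 to 5 contribute 1 each: 2 + 4 = 6. Only the full 5-day schedule exceeds the stated figure.

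**Attempts to reproduce the stated 5:**

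- *End-of-day samples only:* 5 × 1 = 5. This leaves out the baseline draw, which the sentence immediately before the conclusion confirms.
- *Baseline, with no end-of-day draw on day 1:* 1 + 4 = 5. This contradicts the instruction that the end-of-day draw is taken on every day.
- *Four vibration days:* 1 + 4 = 5. This contradicts the permitted 5 days.
- *Before and after on every day:* 2 × 5 = 10. This does not give 5 either, and it contradicts the restriction of pre-vibration draws to day 1.

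No reading consistent with the whole paragraph returns 5.

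**Withheld draws.** With k draws withheld, the count is 1 + d − k. At d = 5, any k of 1 or more gives 5 or fewer. This lowers the count for some patients but does not lower the maximum the schedule permits.

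**Size.** Per patient: 6 − 5 = 1 draw, or 1/5 = 20% above the stated count; 60 − 50 = 10 cc. Across about 50 patients the excess is 0 draws if nobody is sampled on all 5 days. It is at most 50 × 6 − 50 × 5 = 300 − 250 = 50 draws, if everyone is and none is withheld. The documents give no completion or withholding rate, so the total cannot be narrowed further.

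**The case against.** The count itself is not open to dispute; the fair challenge is to its weight. The discrepancy is one 10 cc draw from a catheter already in place, and it arises only at the sixth draw in a patient who completes all 5 days. The Statistical Analysis section is descriptive: summary statistics and curves of response against frequency. It contains no test or sample size that depends on the number of blood samples. The protocol sets no volume limit that 60 cc would breach. One can also read the draw instructions as governing and the maximum as a mis-added summary, or treat 5 as a cap and stop there.

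Most of this stands, and it keeps the consequence small. It does not remove the contradiction. The protocol does not choose between those two readings, and under the cap reading it does not say which sample is given up.

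The hemoglobin rule offers little reassurance. Whether it would ever withhold a draw depends on the intended unit, since the threshold is printed in mg/dl. Nothing in the 6-versus-5 count rests on that rule.

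The cohort total adds little to the argument, because the exposure that matters is per patient.

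**Conclusion.** The concern holds. As written, the schedule permits 6 samples (60 cc) per Phase II patient against a stated maximum of 5 (50 cc by the same arithmetic). The error is exactly one draw and affects only patients vibrated and sampled on all 5 days. The count needs no outside assumption; the volumes assume that every sample is the stated 10 cc. The documents do not show whether 5 was a miscount or an intended cap. It should be corrected because it is a stated limit on research draws in critically ill patients, although the clinical and analytic consequences are minor.

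**What to change.** Change the stated maximum to 6 samples per patient and add the total volume, 60 cc at 10 cc each. If 5 is the intended limit, keep it and name the scheduled draw that is not taken. Dropping an end-of-day draw would be preferable to dropping the baseline, which is the only pre-vibration value.

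Either option is a change to one sentence. Stating 6 makes the declared blood exposure slightly less favorable; keeping 5 gives up one biomarker time point in patients who complete all 5 days.

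### The hemoglobin limit for withholding research blood draws is written in mg/dl, 1000 times below the g/dl value almost certainly meant, so as written it can never apply

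*Combined protocol and SAP*

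**What the plan says.** In the section on potential risks and benefits, item 3 of the risk list is anemia in patient subjects. The mitigation given there is a single sentence: "We will not obtain blood from patients whose last recorded hemoglobin level is less than 8 mg/dl".

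The rule applies to Phase II, which enrolls "critically ill or injured subjects who are expected to experience prolonged immobilization in the intensive care unit". The Phase II measurements include research blood samples of 10 cc each. The schedule, set out just before the risk section, calls for one sample before the first vibration session and one after the last session of each day, for up to 5 days. It concludes: "Thus each patient subject will have a maximum of 5 samples taken during the course of their enrollment". About 50 patients are planned.

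No other section gives a blood hemoglobin limit. The remaining references to hemoglobin, in the Phase I and Phase II measurement lists, concern tissue oxygen saturation, which is a different quantity. The exclusion criteria cover hemodynamic instability and leave room for the care team's judgment, but they name no hemoglobin level.

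**The concern.** Hemoglobin is normally reported in g/dl, and 8 is a workable anemia limit only in that unit. In mg/dl it describes a value incompatible with life. Taken literally, the only hemoglobin-based protection against a risk the protocol itself lists does nothing.

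What is at stake is patient protection and clear conduct of the study. The sentence decides whether blood is drawn for research, repeatedly, from intensive care patients. If it were copied unchanged into a screening form or order set, the check would pass every patient. Anyone monitoring the study against its text would have no usable limit to check.

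**Working it through.** The limit is not derived from other figures in the protocol, so there is no calculation of the plan's own to reproduce. The check is a unit conversion, followed by a rough estimate of how much blood the rule governs.

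**Inputs from the protocol**
- Limit: below 8 mg/dl (risk item 3)
- Volume per draw: 10 cc (Phase II measurements)
- Draws per patient: 5 by the stated maximum, or 1 + 5 = 6 if the written schedule is counted over 5 days
- Patients: about 50

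**Input not in the protocol**
- Blood volume: assumed 4 to 6 L

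**Unit conversion**
- As written: 8 mg/dl ÷ 1000 = 0.008 g/dl
- As presumably meant: 8 g/dl × 1000 = 8000 mg/dl
- Ratio: 8000 ÷ 8 = 1000

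**Effect on the decision, for illustrative hemoglobin values**

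| Hemoglobin (g/dl) | Draw withheld at 8 mg/dl? | Draw withheld at 8 g/dl? |
|---|---|---|
| 4 | No | Yes |
| 5 | No | Yes |
| 6 | No | Yes |
| 7 | No | Yes |
| 7.9 | No | Yes |
| 8 | No | No |
| 10 | No | No |

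The two readings disagree for every patient below 8 g/dl, and those are the patients the rule exists to protect.

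**Amount of blood governed by the rule**
- Per patient: 5 × 10 = 50 cc, or 6 × 10 = 60 cc
- Whole study, at most: 5 × 50 = 250 draws, or 6 × 50 = 300 draws
- Share of blood volume: 50 ÷ 6000 = 0.83% up to 60 ÷ 4000 = 1.5%
- Fall in hemoglobin from 8 g/dl, if the blood is replaced by fluid and no new red cells form: 8 × 0.0083 = 0.07 g/dl up to 8 × 0.015 = 0.12 g/dl

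The 250 to 300 draws are all the draws that could take place. The slip matters only for those in patients below 8 g/dl, and the protocol gives no basis for estimating how many that would be. The difference between 5 and 6 draws is a separate inconsistency. It is carried here only so that the volume is not understated.

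**The case against.** The strongest reply is that the slip corrects itself. The sentence sits under an anemia heading, the literal reading produces a rule that could never apply, and the people drawing blood work in intensive care. Nothing in the protocol suggests that anyone would apply 0.008 g/dl. The total research blood loss is small, and both the cap on samples and the care team's power to exclude a patient remain in force. On this view it is a minor wording correction, and the factor of 1000 measures the typing error, not the harm. Much of this stands: the expected clinical consequence is small, and no count of affected patients can be given.

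It does not remove the point. The investigators judged a hemoglobin limit necessary, and the one they wrote does not work. The sample cap and the exclusion criteria set no hemoglobin level and so do not replace it. A safety threshold should not depend on each reader repairing it.

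Two narrower objections can be granted. The g/dl reading is an inference, though a strong one, which is why the investigator should confirm it. And tying the rule to the most recent recorded value can fairly be read as already covering each draw, so a clause on timing is a clarification and not part of the error.

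**Conclusion.** The concern holds. The written limit is 0.008 g/dl; the value almost certainly intended is 8 g/dl, 1000 times higher. Read literally, no patient would ever be held. That describes the text and does not predict what staff would do.

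The likely harm is small: 50 to 60 cc of blood per patient, or a hemoglobin fall of about 0.07 to 0.12 g/dl from a starting value of 8 g/dl. That range rests on the assumed blood volume of 4 to 6 L and on no new red cells forming during the draws. There is no effect on the statistical analysis. The error should be fixed because it sits in an operative safety rule for critically ill patients, not because it threatens the study's conclusions.

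**What to change.** In risk item 3, replace 8 mg/dl with 8 g/dl after the investigator confirms that 8 g/dl is the intended limit. As an optional clarification, say when the check is made, since draws repeat over up to 5 days. For example: *No research blood will be drawn from a patient whose most recent hemoglobin, checked before each research draw, is below 8 g/dl.* Any screening form or order set that carries the limit should be checked for the same unit.

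The cost is one unit and, if wanted, one short clause. Design, sample size and analysis do not change.

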Testing of a new Therapeutic Vibration Device to reduce neuromuscular weakness in hospitalized patients.

NCT03479008

Approved 3/2/2020

Testing of a New Therapeutic Vibration Device to Reduce Neuromuscular Weakness in Hospitalized Patients

Principal Investigator: [name], University of Michigan: Department of Emergency Medicine

Objective: Test the ability of axial vibration to produce physiologic, biochemical, and anatomic changes consistent with exercise that would help mitigate the development of myopathy associated with prolonged immobilization.

Specific Aims:

- 1) Phase I: In healthy volunteer subjects, test the ability of low frequency vibration at various frequencies to produce muscle contraction activity, tissue oxygenation changes, oxygen consumption changes (only healthy volunteers), biochemical changes, and anatomical changes consistent with moderate physical activity and favorable effects of vibration.
- 2) Phase II: In critically ill patient subjects, test the ability of low frequency vibration at various frequencies to produce muscle contraction activity, tissue oxygenation, biochemical, and anatomical changes consistent with moderate physical activity and favorable effects of vibration.

Background Information:

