During critical illness, patients who are immobilized for more than a few days develop neuromuscular weakness despite receiving full supportive care, which may include physical therapy. In patients requiring mechanical ventilation for longer than 7 days, the incidence of ICU-acquired (neuromuscular) weakness is reported to be between 25% and 60%. Such weakness may contribute to increased duration of mechanical ventilation, increased length of stay in the ICU and hospital, and poor quality of life among survivors. This is part of the newly recognized Post Intensive Care Syndrome (PICS). Moreover, patients who are transferred from the ICU to a high-dependency unit (HDU), intensive therapy unit (ITU), post-operative therapy or outpatient ambulatory care need to be mobile as well as awake for any physical therapy. Patients affected by sepsis, osteoarthritis, spinal cord injury, stroke, multiple sclerosis, cerebral palsy, cancer suffer muscle loss and weakness. Early mobilization (EM) has demonstrated the ability to significantly reduce the detrimental effects of prolonged immobilization such as polyneuropathy and myopathy, which in turn reduces the time patients spend on mechanical ventilation and the overall length of hospital stay. EM treatments include intense physical therapy, cycle ergometry, transcutaneous electrical muscle stimulation (TEMS) and continuous lateral rotational therapy (CLRT). However, scaling of intense physical therapy using therapists is impractical (especially at smaller hospitals) and cannot be implemented in heavily sedated patients. Evidence suggests that whole body vibration may be capable of producing adequate muscle contraction via muscle-spinal loops that may be sufficient to reduce the myopathy and neuropathy of prolonged immobilization thus serving as an effective countermeasure for muscle atrophy.

The purpose of this study is to test a prototype axial vibration device and strategy on its ability to activate large muscle groups, increase muscle blood flow, modulate tissue oxygenation, and increase circulating levels of metabolites associated with exercise/activity. The study will be used to find optimal vibration frequencies that provide maximal signatures associated with muscle and bone stimulation and activity. Eventually we envisage our vibration device to deliver a more effective therapy compared to the incremental gains derived from traditional measures of physical therapy in critically ill patients such

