as TEMS, CLRT and cycle ergometry to patients. It may directly benefit the patient in terms of health, length of stay and reduced re-admission, hospital staff in terms of productivity (i.e., through reduction in nursing effort) and the hospital in terms of improved costs/margins and return on investment. Its utility is also envisioned in many other populations of immobilized acutely ill and injured patients as well as those with chronic conditions.

Muscle response and adaptation to vibrating force seems to be influenced by the characteristics of the input signal, i.e., frequency and amplitude, as well as muscle tension [4]. Experiments carried on the muscle-tendon unit have shown that muscle vibration is a strong proprioceptive stimulus that reaches both the primary somatosensory and motor cortices directly and that the frequency exerts a dependent effect on the Ia afferent firing rate that is reflected in differential frequency-dependent effects on corticospinal motor neuron excitability. Thus, the elevated muscle activity during whole body vibration, rely on the level of vibration and explain how the muscle activity in the lower extremity muscles could be dependent on the changes in the accelerations (i.e., the frequency and/or amplitude) delivered by the device [5].

The therapeutic vibration device we have created is based on a unique design, which has not been utilized by any previous commercial vibration therapy device. The device does not experience loss of vibration intensity and provides the flexibility of multi-dimensional parameter adjustments. It is capable of applying force through the axial skeletal spine, through bidirectional compression loading (or prestressing) between the shoulder and the plantar surfaces of the feet. It is placed around the body like a mobile frame so that the applied vibration can affect the whole body. The vibration actuators (drivers) are mobile and can vary in size, frequency response, and force. The design minimizes the possibility of mechanical interference for ventilated/intubated patients.

The device consists of the following parts:

1. Shoulder cups with inner layer of padding
2. Knee braces with inner layer of padding
3. Leg braces with inner layer of padding
4. Axial pre-stressing system using bands and straps from shoulders to legs
5. Vibration actuators (with amplifiers)

[figure not shown]

Figure 1. Therapeutic vibration device

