The present prototype shoulder cups are built from Nylon 12 with stiffer inner pad lining at the shoulder interfaces. The leg braces, commercially known as PRAFO® Orthosis is a flagship product of M/s Anatomical Concepts, Inc., with a Polyurethane Foam Pad replaceable liner. The adjustable hinged knee braces are commercial off-the-shelf items, supplied by Mueller Sports Medicine, Inc. The hinges of the braces have been flipped to lock the knee joint to ensure maximum transmission of vibration through the bones axially. The resistance bands are also commercially off the shelf items and provide the necessary prestressing. Prestressing of the modular braces using resistance bands is essential to establish a proper fit and an effective vibration transmission. The actuators are driven by amplifiers, which handle all needed frequencies. The current prototype utilizes different size inertial actuators for different parts of the body. The vibration actuators, commercially known as Butt kicker have been sourced from M/s Guitammer Company. The bigger vibration actuators, mounted on the plantar side of the feet operate in the frequency range of 20 Hz – 40 Hz, as it has been identified as an optimal range for the lower part of the body [1-3]. The smaller vibration actuators mounted on the shoulders provide an excitation frequency in the range of 5 Hz -15 Hz, as the range of 7 Hz - 15 Hz for the upper part of the body is considered optimal [1-3].

Replaceable liners will be used between subjects for both knee braces and shoulder cups/leg braces.

Methodology

The modular structure allows us to target the upper, core, and body in combination. Our experiments test both single actuator applications (single frequency) and multiple actuator (multiple frequency) applications. We will test two protocols to identify the optimal frequencies and amplitudes (intensity of vibration) to achieve optimal physiologic responses consistent with moderate physical activity.

Exclusion Criteria (Phase I and II): Acute spinal cord injury, acute vertebral body fracture or injury, acute stroke or intracerebral hemorrhage, hemodynamic instability or other event/condition believed by the care team to warrant nonparticipation, known pregnancy, prisoner

Phase I (Healthy Subjects):

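### The planned analysis relates response to frequency only, so it gives no MFE-STE difference and no loading or amplitude estimate, although the design sets out to study all three

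*Combined protocol and SAP*

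**What the plan says.** The Statistical Analysis section has four sentences. The first promises means or medians with their spread, and percentages. The second promises an effect-response analysis of changing frequency under STE and under MFE. The third defines the display: "Effect-response curves will be constructed with the frequencies on the x-axis and the physiologic response on the y-axis". The fourth says a threshold, glossed as the desired frequency, will be found for individual physiologic changes and for combinations. Frequency is the only explanatory variable named.

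The rest of the document asks for more.

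- **Frequency.** The Specific Aims are to "test the ability of low frequency vibration at various frequencies to produce muscle contraction activity", and Background Information says the study will "find optimal vibration frequencies that provide maximal signatures associated with muscle and bone stimulation and activity". The planned curves fit this.
- **Amplitude.** The general Methodology, before the Phase I heading, states: "We will test two protocols to identify the optimal frequencies and amplitudes (intensity of vibration". Background Information says muscle response seems to be "influenced by the characteristics of the input signal, i.e., frequency and amplitude, as well as muscle tension".
- **Mode.** Methodology states: "Our experiments test both single actuator applications (single frequency) and multiple actuator (multiple frequency) applications". Phase I then says that, to compare MFE with STE, the same subjects will have four to five matched 5-minute episodes, with the application of the two modes randomised.
- **Loading.** Phase I changes band tension to learn how loading alters the response. Loading starts at a weight-based value and may be increased. Phase II takes the optimal loading, as well as frequencies, from Phase I.
- **Baselines.** In Phase I, StO2, VO2 and EMG are each measured before every vibration episode.

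**The concern.** The design pays for information that the stated analysis does not extract. Matched, randomised, within-subject episodes are what one collects to estimate a mode difference, yet none is planned. Loading is varied on purpose and its chosen value is handed to Phase II, yet no loading effect is to be estimated. The frequency curves are also affected: loading differs between episodes and the curves take no account of it, so points at different loadings are pooled.

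MFE raises a further difficulty, because each episode has at least two frequencies at once and the plan does not say which one places it on the axis.

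What is at stake is whether the study can say, with a stated uncertainty, if MFE differs from STE and if loading matters. Without that, the loading carried to critically ill subjects rests on inspection.

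**Working it through.** The plan states no alpha, power, SD or effect size, and gives no derivation for its approximately 50 volunteers. There is therefore no figure to reproduce. The main check sets each question beside its planned analysis.

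| Question | Where it is posed | What Statistical Analysis provides |
|---|---|---|
| Response by frequency | Specific Aims; Background Information | Curves under STE and under MFE |
| MFE against STE | Phase I | Two sets of curves; no difference, no within-subject method, no interval |
| Effect of loading | Phase I; carried into Phase II | Not mentioned |
| Optimal amplitude | General Methodology | Not mentioned |

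**Placing an MFE episode.** The shoulder actuators "provide an excitation frequency in the range of 5 Hz -15 Hz" and the foot actuators run at 20-40 Hz. Take the midpoints as an example: (5 + 15)/2 = 10 Hz and (20 + 40)/2 = 30 Hz. That episode could be plotted at 10 Hz, at 30 Hz, at both, or at the average (10 + 30)/2 = 20 Hz, which neither actuator was delivering. The plan does not choose. For STE the two ranges do not overlap, so one axis separates the sites as long as each actuator stays in its range.

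**What the data could deliver (illustration only).**

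From the documents: 50 subjects with 4-5 episodes each, so 50 × 4 = 200 to 50 × 5 = 250 episodes.

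Assumed, not in the documents: total SD of 1; 2 MFE and 2 STE episodes per subject; within-subject correlation ρ of 0.3 to 0.7; no covariates; no subject-by-mode variation.

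The 95% half-width is 1.96 × √[(1 − ρ)(1/2 + 1/2)/50].

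- ρ = 0.3: 1.96 × √(0.7/50) = 0.232 SD
- ρ = 0.5: 1.96 × √(0.5/50) = 0.196 SD
- ρ = 0.7: 1.96 × √(0.3/50) = 0.152 SD

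These are favourable figures. Suppose the true mode difference itself varies between subjects with SD 0.5 (assumed). At ρ = 0.5 the half-width then becomes 1.96 × √[(0.5 + 0.25)/50] = 0.240 SD. Adding terms for loading, order and frequency would widen it further.

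**The case against.** The strongest reply is that this is pilot work whose aims and purpose centre on frequency, that the frequency analysis is planned for both modes, and that Phase II repeats the tuning, so the Phase I loading is only a starting point. This limits the harm. It does not remove the gap: the protocol says in terms that it will compare the modes and examine loading, and exploratory work still needs an estimate for a question it poses. No hypothesis test or power claim is being asked for.

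It can also be said that the closing reference to combinations covers MFE. It most naturally means combinations of responses. Even read as combinations of frequencies, it supplies no mode contrast and no loading term.

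Four stronger readings are tempting, and the documents do not support them.

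- *Phase I promises to optimise amplitude.* That aim is in the general Methodology. Phase I says only that MFE uses different amplitudes.
- *MFE episodes cannot be plotted.* They can; no method is specified.
- *The pre-episode baselines will be ignored.* The analysis speaks of physiologic changes, which may well mean change from baseline. Their use is simply not stated.
- *Loading is confounded with episode order.* Loading may be increased, and only the application of the two modes is said to be randomised, but no loading schedule is given. Confounding is possible, not shown.

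**Conclusion.** The point holds and should be fixed. It rests on the text alone: the planned analysis has one explanatory variable, while the design deliberately varies mode and loading and the Methodology also seeks optimal amplitudes. Followed as written, the study would return curves comparable by eye, with no MFE-STE difference, no loading or amplitude estimate, and frequency curves pooled over loading.

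The size cannot be computed from the documents. The half-width of about 0.23 to 0.15 SD only indicates that a paired mode estimate could be informative. It depends on the assumed correlation, on two episodes per mode, and on the absence of covariates and of subject-by-mode variation; the model recommended below would give wider intervals.

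A reader might infer that the frequency aim fails or that the Phase II settings are unsound. Neither follows. The STE curves remain interpretable, with the caveat about pooling, and Phase II has its own tuning.

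**What to change.** Record each site's frequency and amplitude, and the loading, for every episode.

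For each main continuous response (StO2, VO2, EMG), fit a simple repeated-measures model with these terms:

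- pre-episode baseline;
- mode (STE or MFE, by active site);
- loading;
- episode order;
- frequency at each active site;
- a subject random effect and, where estimable, a subject-by-mode random effect; otherwise use subject-clustered standard errors.

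Centre each site's frequency and set its term to zero when that site is inactive, so that the mode contrast has a defined meaning.

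Report the within-subject MFE-STE difference against a named STE comparator (foot or shoulder), and the loading effect, each with a 95% CI. Add amplitude as a term if it varies enough; otherwise summarise it descriptively. Show foot and shoulder frequency separately, and show MFE by its frequency pair.

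Leave the loading schedule as the protocol has it. If loading only rises over a session, report its effect as not separable from episode order.

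The cost is a rewritten analysis paragraph, a settings log and a little more analysis, with no new subjects or measurements. The downside is that intervals may be wide, especially for loading.
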